15.2 Reporting requirements

List of abbreviations

AE	Adverse Event
CA	Competent Authority
EC	Ethics Committee
RA	Regulatory authorities
SAE	Serious Adverse Event
SSAR	Suspected Serious Adverse Reaction
SUSAR	Suspected Unexpected Serious Adverse Reaction

15.2.1 AE reporting

Adverse events (AE)

The following information will be recorded:

- nature of adverse event
- date and time of occurrence and disappearance
- intensity: mild, moderate or severe
- frequency: once, continuous or intermittent
- decision regarding study: continuation or withdrawal
- relation to the study medication (see below)

AE's will be recorded from the first drug administration until the patient's last study visit. Special attention will be given to those subjects who have discontinued the trial for an AE, or who experienced a severe or a serious AE.

15.2.2 SAE reporting

Medical events that occur between signing of the Informed Consent and the first intake of trial medication will be documented on the medical and surgical history section and concomitant diseases page of the eCRF.

SAE's occurring within a period of 30 days following the last intake of trial medication will also be handled as such if spontaneously reported to the investigator.

All serious adverse events (SAE) (initial and follow up information – except for those, described in 15.5 and events, described in section [15.2.4](#), and pregnancies occurring during clinical trial must be reported by the local Principal Investigator within 24 hours after becoming aware of the SAE to:

- The national coordinating Investigator
- HIRUZ of the University Hospital Ghent who report to the central EC
- The designated contact person of the Marketing Authorisation Holder (MAH) or producer of the medicinal (investigational) product

This reporting is done by using the appropriate SAE form. For the contact details, see below.

It is the responsibility of the local Principal Investigator to report the local SAE's to the local EC.

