15.1 Definitions

Adverse Events and Adverse Reactions	
Term	Definition
Adverse Event (AE)	Any untoward medical occurrence in a subject to whom a medicinal product is administered and which does not necessarily have a causal relationship with this treatment.
Unexpected Adverse Event	An adverse event of which the nature or severity is not consistent with the Reference Safety Information (RSI) of the product (i.e. the applicable information in the Investigator's Brochure (IB) for an investigational medicinal product which is not authorised or in the Summary of Product Characteristics (SmPC) for an authorised investigational medicinal product).
Adverse Reaction (AR)	An untoward and unintended response in a subject to an investigational medicinal product which is related to any dose administered to that subject. The phrase "response to an investigational medicinal product" means that a causal relationship between a study medication and an AE is at least a reasonable possibility, i.e. the relationship cannot be ruled out. All cases judged by either the reporting medically qualified professional or the Sponsor as having a reasonable suspected causal relationship to the study medication qualify as adverse reactions.
Serious Adverse Event (SAE)	
Any untoward medical occurrence that:
 
 • requires inpatient hospitalisation or prolongation of existing hospitalisation; • results in persistent or significant disability/incapacity; • results in a congenital anomaly or birth defect; • is life-threatening; or • results in death. 
Other important medical events may also be considered serious if they jeopardise the subject or require an intervention to prevent one of the above consequences.
 
NOTE: The term "life-threatening" in the definition of "serious" refers to an event in which the subject was at risk of death at the time of the event; it does not refer to an event which hypothetically might have caused death if it were more severe.

Suspected Unexpected Serious Adverse Reaction (SUSAR)	A serious adverse reaction, the nature, severity or outcome of which is not consistent with the Reference Safety Information (RSI).

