15.2.4 Other reporting requirements

NA

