15.4 Flowchart reporting

Type of Adverse Event	Action(s) be taken
AE	List all relevant AEs per subject in the patient's file and add this information to the CRF.
SAE	
 Notify to HIRUZ CTU and CI within 24 hours after becoming aware of the SAE; Add the SAE to a list that will be reported yearly (see section 15.7); Add the SAE in the CRF (please take into account section 15.5).
SUSAR	
 Notify to HIRUZ CTU and CI within 24 hours after becoming aware of the SAE; The CI/sponsor will assess the causality and unexpectedness of the SAE to determine if it qualifies as a SUSAR. HIRUZ CTU submits the SUSAR to the EMA (through EV database) after communication with the CI; Study team of CI informs company that provides the IMP (as stipulated in the agreement). Coordinating Investigator informs local PIs of safety profile changes.

Reporting to the local ethics committee of SAEs and SUSARs remains the responsibility of the PI and should be done in accordance with the requirements of the local institution's procedure.

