15.5 Events excluded from reporting

NA

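### Non-serious biopsy complications that start before the first dose are not recorded as adverse events, and the 24-hour rule for serious ones is unclear

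*Protocol*

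**What the plan says.** **Timing of the biopsy.** Section 11.4.1 places the ultrasound-guided biopsy at Visit 1B, from week -6 to day -4. Consent is taken at Visit 1A and the first dose is given at Visit 2 (week 0). Addendum 6a describes 10-12 tissue samples through a needle after a lidocaine injection. Section 12 classes the tissue as a research sample for the trial biobank.

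**AE recording.** Under section 15.2.1, AEs "will be recorded from the first drug administration until" the last study visit. The only relatedness item listed there is relation to the study medication. The AE item at Visit 2 covers events after blinded medication has started. The AE row of the Phase A schedule is blank at V1A and V1B.

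**Events between consent and first intake.** Section 15.2.2, under the heading for SAE reporting, opens with: "Medical events that occur between signing of the Informed Consent and the first intake of trial medication will be documented on the medical". The rest of that sentence names the history section and the concomitant-disease page.

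**Serious adverse events (SAEs).** The same section later requires 24-hour reporting by the local Principal Investigator for "All serious adverse events (SAE) (initial and follow up information", apart from events listed in sections 15.5 and 15.2.4. Both of those sections, "Events excluded from reporting" and "Other reporting requirements", read NA. The SAE row of section 15.4 repeats the rule: "Notify to HIRUZ CTU and CI within 24 hours after becoming aware of the SAE".

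**Other biopsy follow-up.** There is a post-biopsy questionnaire at Visit 1B (Addendum 9, available on request) and a biopsy follow-up item at Visit 2.

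**The concern.** Starting AE recording at the first dose suits a comparison of drug effects. It does not suit harm from an invasive research procedure that is always finished before dosing. Under the stated rules, a joint infection or bleed caused by the biopsy needle is entered as the patient's own history. It carries neither the AE intensity grading nor any judgement on whether the procedure caused it.

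What is at stake is patient safety and complete safety reporting:

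- Section 4.2 weighs drug risk and does not discuss the biopsy.
- No DSMB is foreseen (section 15.6), and the reason given is the known safety profile of the IMP together with the trial design.
- The annual safety report (section 15.7) is to include all SAEs, so it depends on sites recognising a pre-dose event as reportable.

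**Working it through.** No power, alpha or rate calculation applies. The check sets the passages side by side.

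**1. Can a biopsy complication start before dosing?** The Visit 1B window opens 6 × 7 = 42 days before the first dose and closes 4 days before it. Every biopsy therefore precedes dosing by at least 4 days, and a complication can start in that gap.

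**2. Is a non-serious one recorded as an AE?**

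| Provision | Effect on a pre-dose, non-serious biopsy event |
|---|---|
| 15.2.1, start of recording | Not yet open |
| 15.2.1, relatedness | Study medication only; no procedure item |
| Visit 2 AE item | Only events after blinded drug has started |
| Phase A schedule, AE row | No mark at V1A or V1B |
| 15.2.2, opening sentence | History and concomitant-disease pages; no exception for procedure-related events |

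All five agree, so the event is not recorded as an AE. Someone might take the lidocaine injection as the first drug administration in 15.2.1. The Visit 2 item and the schedule show that study medication is meant.

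**3. Does the AE definition exclude the event?** No. Section 15.1 defines an AE as "Any untoward medical occurrence in a subject to whom a medicinal product is administered". Lidocaine is a medicinal product, and the wording does not limit itself to an investigational one. The recording window and the history rule keep the event out, not the definition.

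**4. What about a biopsied patient who is never dosed?** Eligibility is checked again at Visits 1B and 2. Section 8.2.1.1 includes a baseline examination to exclude spontaneous remission. Under section 8.5 a screen failure is not enrolled, and only a minimal set of information is kept. There is no first dose, so the window in 15.2.1 never opens.

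**5. Do the questionnaire and the Visit 2 follow-up close the gap?** They collect some information. No passage in the document says that a finding from either is to be entered as an AE or SAE.

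**6. Is a serious one notified within 24 hours?**

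- *Towards notification:* the 15.2.2 sentence on all SAEs; the SAE row of 15.4, which has no first-dose condition; the SAE criteria in 15.1 (for example, "requires inpatient hospitalisation or prolongation of existing hospitalisation"), which are not tied to drug intake; and the empty lists in 15.2.4 and 15.5.
- *Towards history only:* the opening sentence of 15.2.2 stands under the SAE heading and makes no exception for serious events. The next sentence also frames SAE handling by drug intake, covering 30 days after the last intake.
- *Not stated:* when SAE reporting starts, and whether the history entry is in addition to notification or replaces it.

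The first group is the stronger reading, but the protocol leaves the reader to work it out.

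**The case against.** **Recording from the first dose is an explicit, consistent convention.** This is true: 15.2.1, Visit 2 and the schedule agree with one another. The point on non-serious events is therefore about a poorly chosen rule, not a contradiction. The convention still does not fit a research procedure that always comes before dosing.

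**The events are captured elsewhere.** This is partly right. There are history pages, a questionnaire, a Visit 2 follow-up, and observation of up to 30 minutes with advice to call. The questionnaire's content is not shown and could hold severity items or escalation instructions. What stands is that nothing visible in the protocol links these sources to AE or SAE reporting.

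**The serious case is already covered.** A reader might infer that the two sentences of 15.2.2 contradict each other, or that serious biopsy complications go unreported. The documents do not support either inference. Entering an event in the history and notifying it within 24 hours are compatible, the history sentence does not say that it replaces notification, and no event category is exempted. What remains is an unclear start of the reporting window. A site could in good faith make only the history entry.

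**Few patients are concerned.** This may be so. Only biopsied patients with a complication that starts before dosing are affected, and the biopsies are done at three named units.

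**Conclusion.** The point holds in two parts of unequal strength.

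- **Non-serious events (firm).** By the stated rules, a biopsy complication that starts before the first dose is not recorded as an AE. For a biopsied screen failure, AE recording never opens.
- **Serious events (a lack of clarity).** The better reading requires 24-hour notification, but the protocol neither states the start of the SAE window nor says how the history rule relates to it. The annual safety report would miss such an event only if a site took the history-only reading.

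The size cannot be given as a count or a share, because the document states neither how many patients are biopsied nor a complication rate. A reader might try to derive a share from the days in Addendum 6a within which patients are advised to call. Those days are aftercare advice and not a risk period, so any such figure would describe calendar overlap and not events.

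A reader might also infer that the safety comparison between arms is distorted. It is not, because these events come before treatment. The primary and secondary analyses are untouched. The conclusion rests on the visible text only; Addendum 9 and the eCRF were not available. This is a patient-safety and reporting matter that should be corrected, and not a threat to the trial's main result.

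**What to change.** Amend sections 15.2.1 and 15.2.2 and the Phase A schedule as follows.

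1. Record events related to a study procedure (biopsy, local anaesthetic, research blood draw) as AEs from consent, with a procedure-relatedness item beside the drug-relatedness item. Mark the AE row of the schedule accordingly.
2. State in 15.2.2 when SAE reporting starts, and that serious procedure-related events follow the existing 24-hour route, biopsied screen failures included.
3. Limit history-only filing to pre-dose events that are both non-serious and unrelated to a study procedure.
4. State that findings from the post-biopsy questionnaire and the Visit 2 biopsy follow-up that qualify as an AE or SAE are entered as such.
5. List procedure-related events separately from treatment-emergent ones.

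The cost is protocol wording, one eCRF field, use of the existing AE and SAE forms at Visits 1B and 2, and a few more reports. The treatment-emergent comparison does not change.

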15.2.3 SUSAR reporting

In case the Coordinating Investigator/sponsor, in consultation with HIRUZ CTU, decides the SAE is a SUSAR (considering the seriousness, probability of harmfulness and unexpectedness), HIRUZ CTU will report the SUSAR to the EMA, through the Eudravigilance (EV) database within the timelines as defined in European legislation. In case of a life-threatening SUSAR the sponsor should report at least the minimum information as soon as possible and in any case no later than 7 calendar days after being made aware of the case. In case of a non-life-threatening SUSAR the reporting process must be completed within 15 calendar days.

Coordinating Investigator informs local PIs of safety profile changes, not of individual SUSAR reports. For example, information derived from SUSAR reports could be

provided via investigators' letters including both an updated benefit-risk evaluation and risk mitigation measures.

15.2.4 Other reporting requirements

NA

15.4 Flowchart reporting

Type of Adverse Event	Action(s) be taken
AE	List all relevant AEs per subject in the patient's file and add this information to the CRF.
SAE	
 Notify to HIRUZ CTU and CI within 24 hours after becoming aware of the SAE; Add the SAE to a list that will be reported yearly (see section 15.7); Add the SAE in the CRF (please take into account section 15.5).
SUSAR	
 Notify to HIRUZ CTU and CI within 24 hours after becoming aware of the SAE; The CI/sponsor will assess the causality and unexpectedness of the SAE to determine if it qualifies as a SUSAR. HIRUZ CTU submits the SUSAR to the EMA (through EV database) after communication with the CI; Study team of CI informs company that provides the IMP (as stipulated in the agreement). Coordinating Investigator informs local PIs of safety profile changes.

Reporting to the local ethics committee of SAEs and SUSARs remains the responsibility of the PI and should be done in accordance with the requirements of the local institution's procedure.

15.5 Events excluded from reporting

NA

15.6 Data Safety Monitoring Board (DSMB)

All IMP is authorised and used in current practice. Considering the known safety profile of the IMP and trial design, a DSMB is not foreseen.

15.7 Annual Safety Report (ASR)

The Coordinating Investigator will provide an ASR once a year throughout the entire duration of the clinical study, or on request, to the EMA.. This ASR will include all SAEs and relevant safety information regarding all investigational medicinal products, used in this trial.

The report will be submitted no later than 60 calendar days after the ASR Data Lock Point (DLP). The first DLP is 1 year after the first date of the sponsor's authorisation to conduct the clinical trial. Subsequently, the ASR will be submitted each year (+ maximum 60 days) until the trial is declared ended.

The Coordinating Investigator provides the ASR to all local PIs.

15.8 Follow-up after an adverse reaction

After the initial AE/SAE report, the investigator must proactively follow each participant at subsequent visits/contacts. The investigator is obligated to perform or arrange for the conduct of supplemental measurements and/or evaluations as medically indicated or as requested to elucidate the nature and/or causality of the AE or SAE as fully as possible. All SAEs as defined in Section 15.1, will be followed until resolution, stabilization, the event is otherwise explained, or the participant is lost for follow-up (defined in Section 8.3)

16 Monitoring, audits and inspections

16.1 Monitoring

16.1.1 General

Monitoring of the trial will be performed in compliance with GCP E6(R2) and the applicable regulatory requirements. The study team will be trained during an initiation visit by the monitor. A detailed description of the monitoring tasks can be found in the latest version of the (study-specific) 'Clinical Trial Monitoring Plan'.

16.1.2 Monitoring team

Monitoring services will be provided by HIRUZ CTU. All relevant contact details (e.g. primary contact person) can be found in the 'Clinical Trial Monitoring Plan'.

16.1.3 Scope

Monitoring services will consist of the following (non-exhaustive list):

- review of informed consents and the followed process;
- check on recruitment status;
- checking for protocol deviations/violations;
- checking GCP compatibility;
- check on safety reporting compliance;
- IMP handling and storage;
- review of study data.

More information can be found in the Clinical Trial Monitoring Plan.

16.2 Inspection

This trial can be inspected at any time by regulatory agencies during or after completion of the trial. Therefore access to all study records, including source documents, must be accessible to the inspection representatives. Subject privacy must be respected at all times, in accordance to GDPR, GCP and all other applicable local regulations.

The investigator/study team should immediately notify the sponsor if (s)he has been contacted by a regulatory agency concerning an upcoming inspection.

16.3 Deviation policy

Sponsor and all investigators agree to take any reasonable actions to correct protocol or other deviations/violations noted during monitoring/inspection, in consultation with the monitoring team. All deviations must be documented on the correct deviation log by the study team that is kept available at any time for monitoring/inspection purposes. Subject deviations must be reported in the eCRF. Site deviations and sponsor deviations must be reported on the paper Site Deviation Log and Sponsor Deviation Log, respectively, and each deviation has to be signed off. Under emergency circumstances, deviations from the protocol to protect the rights, safety or well-being of human subjects may take place without prior approval of the sponsor and the RA.

16.4 Serious breach to GCP and/or the protocol

A 'serious breach' means a breach likely to affect to a significant degree the safety and rights of a subject or the reliability and robustness of the data generated in the clinical trial.

Any deviation of the approved protocol version or the CTR that is likely to affect subject safety, data integrity and/or study conduct should be clearly documented on the applicable deviation log and will be communicated with the Coordinating Investigator, HIRUZ CTU and possibly the RA.

Please contact HIRUZ CTU immediately in case of a potential serious breach:

The sponsor shall notify the RA about a serious breach of the CTR or of the version of the protocol applicable at the time of the breach through the EU portal without undue delay but not later than seven days of becoming aware of that breach.

Early termination of the trial (in a specific center or overall) may be necessary in case of major non-compliance.

The following items will be documented on the protocol deviation log: date of deviation, description of deviation, actions taken and classification of deviation. Deviations will be classified as minor or major. A minor protocol deviation is a deviation that does not affect the safety, rights or well-being of subjects or the quality of their data. A major protocol deviation is a deviation that affects safety, rights or well-being of subjects or quality of their data.

Any deviation that potentially interferes with and/or affects the efficiency and/or quality conduct of the study will be discussed by the monitor with the PI and will be documented on the monitoring report including a proposed plan of action for resolution if applicable.

16.5 Early termination

Early termination or suspension of the study or an investigational site may be necessary in case of major non-compliance, critical safety issues or premature trial discontinuation. This can occur at any time by the sponsor, principal investigator of the local site, EC or regulatory authority. In the event that the clinical investigation would be discontinued prematurely, all clinical investigation products will be retained, the terminating party shall justify its decision in writing and the sponsor will communicate (via Hiruz CTU) early termination, including the reason for early termination, to the EC and regulatory authority.

17 Ethical and legal aspects

17.1 Good Clinical Practice

The trial will be conducted in accordance with the latest version of the ICH E6 (R2) GCP guidelines, creating a standard for the design, conduct, performance, monitoring, auditing, recording, analyses and reporting of clinical studies that provides assurance that the data and reported results are accurate and that the rights, integrity and confidentiality of study subjects are protected.

17.2 Informed consent

Eligible subjects may only be included in the trial after providing written (witnessed, if needed) IEC-approved informed consent, or, if incapable of doing so, after such consent has been provided by a legally acceptable representative(s) of the subject. Informed consent must be obtained before conducting any study-specific procedures (as described in this protocol).

Prior to entry in the trial, the investigator must explain the trial and the implication(s) of participation to potential subjects and/or their legal representatives. Subjects will be informed that their participation is voluntary and that they may withdraw consent to participate at any time. Participating subjects will be told that their records may be accessed by competent authorities and by authorised persons without violating the confidentiality of the subject, to the extent permitted by the applicable law(s) and/or regulations. By signing the Informed Consent Form (ICF), the subjects or legally acceptable representatives are authorising such access.

After this explanation and before entry to the trial, written, dated and signed informed consent should be obtained from the subject or legally acceptable representative. The ICF should be provided in a language sufficiently understood by the subject. Subjects must be given the opportunity to ask questions.

The subject or legally acceptable representative will be given sufficient time to read the ICF and to ask additional questions. After this explanation and before entry to the trial, consent should be appropriately recorded by means of either the subject's or his/her legal representative's dated signature or the signature of an independent witness who certifies the subject's consent in writing. After having obtained the consent, a copy of the ICF must be given to the subject.

In case the subject or legally acceptable representative is unable to read, an impartial witness must attest the informed consent.

Subjects who are unable to comprehend the information provided can only be enrolled after consent of a legally acceptable representative.

The following information should be added to the electronic patient dossier (EPD):

- which version of the ICF was obtained;
- who signed the ICF;
- if sufficient time has been given to consider participation into the trial;
- which investigator obtained ICF with the date of signature;
- if a copy was provided to the subject;
- start and end of participation in the trial.

